#### 9.2 Patient Accrual and Expected Duration of Trial

Patients will be continually accrued until a target of 50 methotrexate infusions requiring any protocolprescribed dose adjustments are reached. The expected duration of accrual for the trial is 2-2.5 years.

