#### GOALS AND OBJECTIVES

### 1.1 Primary Aim

To determine the incidence of successfully achieving peripheral blood concentration of methotrexate of 50-80µM in patients at high risk of drug toxicity after a 24 hour infusion of high-dose methotrexate treated according to our institutional treatment algorithm for individualized methotrexate dosing.

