### 1.3 Hypothesis

At least eighty percent of patients with a high risk for or past history of significant methotrexate toxicity, receiving 24-hour high-dose methotrexate infusions per this institutional algorithm for individualized dosing will have an appropriately therapeutic but minimally toxic 24 hour methotrexate level between 50-80µM.

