Based largely on the previous work at SJCRH, we developed an individualized methotrexate treatment plan as an option to safely administer HDMTX, with a target Cpss of 65 μM to patients at risk for delayed clearance and subsequent toxicity. Other options for this population would include a 25% methotrexate dose reduction or complete omission of HDMTX from their treatment. Since 2007. Texas Children's Hospital (TCH) has given patients with past history of toxicities including renal toxicities individualized methotrexate with no known increase in toxicities based on evolving versions of this treatment plan (n =14 patients; ref: personal communications with faculty members of the Texas Children's Hospital Leukemia Program). Work by Aumente, et al, demonstrated that the Monte Carlo simulated MTX concentration and means over time show a peak methotrexate concentration near hour 2, with steady state occurring near hour 6. Therefore, our treatment plan provides guidelines for HDMTX dose adjustments based on hour 2 and 6 methotrexate levels. In addition, these adjustments are based on a fixed, simple bed-side algorithm and thus avoid the need for complex pharmacokinetic modeling. Patients treated according to the algorithm may thus not need their dose altered. With this in mind, in addition to our eligibility criteria we will allow attendings to enroll patients as they deem necessary, since if the MTX Cpss is therapeutic no alterations to therapy will be made. In September, 2012, this treatment plan was formalized and approved for clinical use by the Texas Children's Cancer Center Chemotherapy Safety Committee.

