#### 4. TREATMENT PLAN

#### 4.1 Overview of Treatment Plan

Our prospective study will enroll patients who will receive HDMTX given as a 5g/m² 24-hour infusion. Enrolled patients will be receiving HDMTX as determined by their primary provider. Patients are eligible to be enrolled at any time point during their treatment course, and may participate during any one or more of their multiple HDMTX administrations.

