- 1b) Explore potential changes in incidence of success (achieving an end infusion peripheral blood MTX concentration between 50-80  $\mu$ M) between sequential administrations of HDMTX. The primary endpoint and sample size calculation refer to the first cycle for each patient.
- Aim 2 2a) Calculate the frequency of adverse effects after each infusion. Success rate over multiple cycles within individual patients will be analyzed using generalized estimating equations for binary outcomes. This method will also be applied to the frequency of adverse events and to the assessment of factors associated with outcome. Continuous and ordinal/non-normal adverse effects will be compared via paired t-test or Wilcox sign rank test respectively.
- 2b) Describe the genotype of various methotrexate metabolizing SNPs in each subject. The polymorphisms of subjects in this study will be compared to published minor allele frequencies and when appropriate will be stratified by race/ethnicity. The purpose of this analysis will be to describe trends away from the major allele frequency in patients known to either have experienced or who are at high risk for developing adverse effects to HDMTX.
- 2c) Examine predictors of success of achieving a  $CP_{ss}$  of 50-80  $\mu$ M. Variables in our analysis will include (but not be limited to) age, sex, disease type, race/ethnicity and measure of pre-MTX renal function. An analysis both with and without SNP genotype will be performed secondary to the likelihood that race/SNP correlations will interfere with SNPs being a truly independent variable. We will initially use chi-square test for group variables and t-test for continuous variables. Logistic regression will be used for multivariable analysis to control for confounders and estimation of adjusted odds ratios. P<0.05 will be considered statistically significant.

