# 9.3 Statistical Analysis Methods

Sample size with power justification:

Sample size is estimated on primary study objective of estimating the true rate of success with the new protocol. Success is defined as 80% of infusions achieving 24hr HDMTX end infusion MTX values of  $50\text{-}80\mu\text{M}$ . A sample size of 50 methotrexate infusions per the algorithm produces a two-sided 95% confidence interval with a width equal to 0.22 when the sample proportion is 80%. We will be 95% confident that the true success rate in the study would be between 69% and 91%.

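### Sections 9.1, 9.2 and 9.3 count three different units, so the accrual rule does not assure the planned 0.22-wide interval (69% to 91%)

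*Combined protocol and SAP*

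**What the plan says.** Three sections describe the sample size in three ways.

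- **Section 9.1, Aim 1b:** "The primary endpoint and sample size calculation refer to the first cycle for each patient". The hypothesis in 1.3 is also per patient: "At least eighty percent of patients with a high risk for or past history of significant methotrexate toxicity".
- **Section 9.2:** "Patients will be continually accrued until a target of 50 methotrexate infusions requiring any protocolprescribed dose adjustments are reached". The unit is the dose-adjusted infusion.
- **Section 9.3:** "A sample size of 50 methotrexate infusions per the algorithm produces a two-sided 95% confidence interval with a width equal to 0.22", at a sample proportion of 80%. It then gives 69% to 91% as the range for the true rate. The criterion is per infusion: "Success is defined as 80% of infusions achieving" the target range. The unit is any infusion under the algorithm.

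The last two sets differ, because section 2.4 says "Patients treated according to the algorithm may thus not need their dose altered". Section 4.1 lets a patient contribute more than once: patients "may participate during any one or more of their multiple HDMTX administrations", may re-enroll without new consent, and are followed on a schedule that allows for four doses. Sections 9.1 and 9.3 plan generalized estimating equations (GEE) for success over multiple cycles.

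The word *cycle* has two uses. The re-enrollment sentence in 4.1 fits a single infusion. The analysis text in 9.3 (item 1b) uses it for a block in which infusions are given every two weeks.

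**The concern.** The interval width is the plan's only sample-size justification. It holds if 50 independent observations enter the primary analysis. Section 9.1 says those observations are first cycles, but the rule that ends accrual counts something else. Fifty adjusted infusions can come from fewer than 50 patients (through repeats) or from more than 50 (where many infusions need no adjustment). A reader of 9.3 cannot tell how many patients will support the headline success rate, and the choice between first, adjusted and all infusions is not tied down in one place.

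**Working it through.** **Step 1: reproduce the plan's figure.** Inputs from 9.3: p = 0.80, n = 50, two-sided 95%. Wald interval: 0.80 ± 1.96 × √(0.8 × 0.2/50) = 0.80 ± 0.111, that is 0.689 to 0.911, width 0.222. This matches 0.22 and 69% to 91%. For 40/50 the alternatives do not give both figures: Wilson 0.670 to 0.888, Agresti-Coull 0.668 to 0.890, Jeffreys 0.674 to 0.892, Clopper-Pearson 0.663 to 0.900. So 9.3 uses Wald with no design effect, which treats the 50 observations as independent.

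**Step 2: first cycle read as the first on-study infusion.** Let f be the share of infusions adjusted and m the mean infusions per patient. When 50 adjusted infusions have accrued, total infusions are about 50/f and patients about n = 50/(f × m). Width = 2 × 1.96 × √(0.16/n), with n rounded up. Neither f nor m is given for this trial. The middle row borrows the 58% in section 2.4, a per-patient rate from an earlier study that used pharmacokinetic modelling, so it is only an illustration. The range 0.4 to 0.8 is also an assumption.

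| f | m = 1 | m = 1.5 | m = 2 | m = 3 | m = 4 |
|---|---|---|---|---|---|
| 0.4 | n=125, 0.14 | n=84, 0.17 | n=63, 0.20 | n=42, 0.24 | n=32, 0.28 |
| 0.58 | n=87, 0.17 | n=58, 0.21 | n=44, 0.24 | n=29, 0.29 | n=22, 0.33 |
| 0.8 | n=63, 0.20 | n=42, 0.24 | n=32, 0.28 | n=21, 0.34 | n=16, 0.39 |

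The break-even is f × m = 1, which gives n = 50. Below it the interval is narrower than planned, above it wider. For m of 1 to 2 the width runs from 0.14 to 0.28. A mean near 4 is an outer limit: enrollment may begin at any point in treatment and re-enrollment is optional (4.1), and grade 3 or higher renal or neurologic toxicity ends protocol therapy (7.1.1).

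**Step 3: first cycle read as a block of two-weekly infusions.** Infusions within a patient are then correlated. With intra-patient correlation ICC (not in the documents, assumed 0.1 to 0.5), the design effect is 1 + (m − 1) × ICC, and for 50 infusions the width is 2 × 1.96 × √(0.16 × design effect/50).

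| Infusions per patient | ICC 0.1 | ICC 0.3 | ICC 0.5 |
|---|---|---|---|
| 2 | 0.23 | 0.25 | 0.27 |
| 3 | 0.24 | 0.28 | 0.31 |
| 4 | 0.25 | 0.31 | 0.35 |

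This takes 9.3's 50 infusions as the analysed number. If unadjusted infusions are added on top of 50 adjusted ones, the number is 50/f and each width is multiplied by √f (0.63 at f = 0.4, 0.89 at f = 0.8). The count is again not fixed by the plan.

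**The case against.** The best defence is that 9.1 governs the 50 in 9.2 and 9.3. On that reading accrual runs to 50 adjusted first infusions, unadjusted first infusions come on top, n is at least 50 and the width is at most 0.22. But this adds a first-cycle limit that 9.2 does not state, in a protocol that expressly allows repeat infusions. It may be what was meant, but it is not what is written.

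A second defence is that the GEE deals with repeats. It gives a valid standard error for pooled infusions. It does not fix the number of patients, and it does not restore the planned width for a first-cycle endpoint.

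Three objections stand. The tables rest on assumed f, m and ICC. Each table holds under one meaning of *cycle* only, and the text does not settle which. The final interval will use the observed data, and no test or decision rule uses the width.

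A reader might go further in two ways. One is to infer that the trial will be less precise than planned, with perhaps 13 patients (50/4 = 12.5, width about 0.44). That needs every infusion adjusted and every patient giving four, which the documents do not suggest; precision can equally be better than 0.22. The other is to infer that only adjusted infusions form the primary set. The primary aim covers patients "treated according to our institutional treatment algorithm for individualized methotrexate dosing", and section 2.4 expects some of them to need no change, so the text points to all algorithm-treated patients.

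**Conclusion.** The point holds as a mismatch between the primary unit (9.1), the accrual rule (9.2) and the planning width (9.3). The arithmetic in 9.3 is right for 50 independent observations, but the accrual rule does not secure that number. The size is conditional: a width of 0.14 to 0.28 if the unit is the first on-study infusion (f of 0.4 to 0.8, m of 1 to 2, all assumed), or about 0.23 to 0.35 for 50 infusions if a cycle is a block (2 to 4 infusions per patient, ICC of 0.1 to 0.5, all assumed). Not even the direction of the error is established. The harm is a misstated planning precision. The documents do not support a claim of a wrong conclusion or an invalid analysis. It should be fixed because it concerns the only sample-size justification and the correction is cheap.

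**What to change.** 1. In 1.3 and 9.1 to 9.3, state one primary unit and set, for example the first on-study infusion of every patient who starts the algorithm, adjusted or not.
2. Define *cycle* once and use it the same way throughout.
3. Say how patients removed under 7.1.3 (levels not available in time) and 7.1.4 (long interruption) count in the denominator.
4. Keep the accrual stop in 9.2. The number of primary observations then stays open, so in 9.3 replace the single 0.22 and the 69% to 91% sentence by an illustrative table over the possible number of patients, and name the interval method. Wilson is suggested because Wald limits can pass 100% at small n (at n = 13 the upper limit is 101.7%). Wilson 95% at an observed 80%:

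| Patients | 95% interval |
|---|---|
| 16 | 55.7% to 92.7% |
| 30 | 62.7% to 90.5% |
| 50 | 67.0% to 88.8% |
| 80 | 70.0% to 87.3% |
| 125 | 72.1% to 86.1% |

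5. Analyse all infusions as secondary with the GEE already planned.

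The cost is wording and one small table, with no extra patients. The downside is that the stated precision may look less favourable than 0.22.

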# 9.3 Statistical Analysis Methods

Sample size with power justification:

Sample size is estimated on primary study objective of estimating the true rate of success with the new protocol. Success is defined as 80% of infusions achieving 24hr HDMTX end infusion MTX values of  $50\text{-}80\mu\text{M}$ . A sample size of 50 methotrexate infusions per the algorithm produces a two-sided 95% confidence interval with a width equal to 0.22 when the sample proportion is 80%. We will be 95% confident that the true success rate in the study would be between 69% and 91%.

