The interventions in this protocol occur at the 2 and 6 hour (or 8 hour if the 2 hour level was  $\geq 100 \mu M$ ) time points. After the 24hr HDMTX infusion is complete, the individualized protocol will end and patients will remain on study but be off of the protocol therapy. After this time, management of MTX levels will continue according the treating physician's discretion using standard supportive care guidelines. This is elaborated below in Appendix B, suggested supportive care guidelines based on the COG algorithm. Interventions for toxicity are at the discretion of the treating provider as patients will be off treatment protocol at the 24hr time point. Glucarpidase should be administered based on the treating physician's discretion, with the recommendation that it be administered prior to the development of grade 4 nephrotoxicity and prior to 96 hours after the start of the HDMTX infusion. Administration of CPDG2 after these time points have been shown to be statistically associated with the development of  $\geq$  grade 4 toxicity.

Patients may be re-enrolled on this protocol therapy again for subsequent HDMTX infusions without the need for re-consent. In order to re-enroll, call the study coordinating center as outlined in Section 3.1 PRIOR to the cycle in which the dose modification protocol will be implemented.

The active length of study participation for each patient is 4 weeks after the last high-dose methotrexate infusion or until the next cycle of chemotherapy begins (which ever occurs first). Therefore, the maximum amount of active time on study would be 2.5 months. This would include 4 doses of HDMTX given every other week plus a 4 week follow-up period to assess for side effects.

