#### 7. CRITERIA FOR REMOVAL FROM PROTOCOL THERAPY AND OFF STUDY CRITERIA

- 7.1 Removal from Protocol Therapy
  - 7.1.1 ≥ Grade 3 renal or neurologic toxicity
  - 7.1.2 Parent/patient or provider request
  - 7.1.3 Inability to analyze methotrexate levels at given time points. Patients will come off of study secondary to the inability to make dose modification decisions if methotrexate levels at required time points are not available within 120 minutes of drawing the level. If this occurs, treatment decisions will be up to the treating physician. Options would include: discontinuing the methotrexate infusion, altogether or calculating a 25% total dose reduction (as suggested by COG) and stopping the infusion when the total dose given reaches the newly calculated reduced dose.
  - 7.1.4 Methotrexate infusion interrupted for longer than 2 hours.
- 7.2 Off Study Criteria
  - 7.2.1 Lost to follow-up
  - 7.2.2 4 weeks after the end of methotrexate infusion or start of next chemotherapy, which ever is shorter.
  - 7.2.3 Death
- 8. Data Monitoring

Texas Children's Cancer Center, where we will be conducting our research, is part of the Dan L. Duncan Cancer Center (DLDCC). The NCI-designated Dan L. Duncan Cancer Center at Baylor College of Medicine is a consortium made up of several institutions across the Texas Medical Center. As part of the DLDCC, we will have access to various shared resources, including a Clinical Trials Support Unit. For our data monitoring, we will utilize the Data Safety and Monitoring Committee (DSMC) through the DLDCC.

- 8.1. Stopping rules
  - 8.1.1. Two patients with HDMTX induced nephropathy necessitating dialysis or administration of carboxypeptidase.
  - 8.1.2. Two patients achieving a 24 hour  $Cp_{ss}$  of <20 $\mu$ M.
  - 8.1.3. Two patients needing intensive care admission for HDMTX related toxicities.
  - 8.1.4. Any death attributed to HDMTX toxicity.

If any of the above criteria are met then the study will be stopped, the incident(s) will be reviewed, and the study will be amended to address the incident(s) prior to potentially re-opening.

- 9. Statistical Considerations
- 9.1 Statistical Design

Aim 1 1a) Calculate the incidence of success with the new protocol (achieving an end infusion

Protocol Version 8.0 Date: June 17, 2015

peripheral blood MTX concentration between 50-80 μM)

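### Section 9.3's 69%–91% interval assumes 50 independent infusions, but the primary endpoint is one first cycle per patient and the number of patients is not fixed

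*Combined protocol and SAP*

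**What the plan says.** **Precision.** Section 9.3 gives the purpose as estimation: "Sample size is estimated on primary study objective of estimating the true rate of success with the new protocol". It takes 50 infusions treated per the algorithm and a sample proportion of 80%, and states a two-sided 95% interval of width 0.22. It then adds: "We will be 95% confident that the true success rate in the study would be between 69% and 91" per cent. No interval method is named.

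**Unit.** Section 9.1 says: "The primary endpoint and sample size calculation refer to the first cycle for each patient". Section 9.2 counts something else: "Patients will be continually accrued until a target of 50 methotrexate infusions requiring any" protocol-prescribed dose adjustment. Section 4.1 allows repeat participation: "Patients may be re-enrolled on this protocol therapy again for subsequent HDMTX infusions without the need for re-consent".

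**Definition of success.** Section 9.3: "Success is defined as 80% of infusions achieving 24hr HDMTX end infusion MTX values of" 50–80 µM. Section 9.1, and the Analysis part of 9.3, treat success as a single end-infusion level in that range. Section 1.3 hypothesises that at least 80% of patients will be in range.

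**Aim 1a.** Section 1.1 reads "To determine the incidence of successfully achieving peripheral blood concentration of methotrexate" in the target range, and section 9.1 reads "Calculate the incidence of success with the new protocol". The Analysis part of 9.3 instead words Aim 1a as an overall change in that incidence. It places 1a in one sentence with 1b and 1c, and that sentence ends by assigning generalized estimating equations (GEE).

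**The concern.** A binomial interval on 50 needs 50 independent observations. Infusions from the same patient are not independent, and the accrual rule fixes neither the number of patients nor the number of first cycles. The precision actually obtained for the primary endpoint could therefore be clearly worse than printed, or somewhat better, and the plan does not tell the reader which.

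The interval method for the final result is also left open. At high success rates the choice can decide whether the lower limit clears 80%, the value in the hypothesis. Finally, the sentences that should define the outcome and the primary analysis do not match the aims they serve, so more than one analysis could later be called the primary one.

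**Working it through.** **Inputs.** From section 9.3: n = 50, observed proportion 0.80, two-sided 95% (z = 1.96), width 0.22, limits 69% and 91%. From section 1.3: the 80% hypothesis. Patient numbers other than 50 are my assumptions, because the plan gives none.

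**1. The plan's own figure.** Wald: p ± z·√(p(1−p)/n) = 0.80 ± 1.96·√(0.8·0.2/50) = 0.80 ± 0.111, giving 0.689 to 0.911, width 0.222. This reproduces the plan. At 40/50 other methods do not give both limits: Wilson 0.670–0.888 (width 0.218), Clopper-Pearson 0.663–0.900 (0.237), Agresti-Coull 0.668–0.889 (0.222), Jeffreys 0.674–0.892 (0.218).

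**2. Precision by number of first-cycle patients.** Wilson: [p + z²/2n ± z·√(p(1−p)/n + z²/4n²)] / (1 + z²/n), at p = 0.80.

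| Patients | In range | Wilson 95% CI | Width |
|---|---|---|---|
| 25 | 20 | 61%–91% | 0.30 |
| 30 | 24 | 63%–90% | 0.28 |
| 40 | 32 | 65%–90% | 0.24 |
| 50 | 40 | 67%–89% | 0.22 |
| 60 | 48 | 68%–88% | 0.20 |

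Twenty-five patients corresponds to two counted infusions each (50/2). Sixty is possible because infusions that need no adjustment do not count towards the 50 in section 9.2.

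**3. Does the method matter?** Exact binomial sums for 50 independent patients:

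| True rate | Wald coverage | Wilson coverage | Wald: lower limit above truth | Wilson: same |
|---|---|---|---|---|
| 0.79 | 95.6% | 96.5% | 3.4% | 1.2% |
| 0.80 | 93.8% | 95.1% | 4.8% | 1.9% |
| 0.81 | 91.3% | 93.2% | 6.7% | 2.7% |
| 0.85 | 94.1% | 95.6% | 4.6% | 1.4% |
| 0.90 | 87.9% | 97.0% | 11.2% | 0.5% |

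The nominal value for the last two columns is 2.5%. At 45/50 the lower limit is 81.7% with Wald, 78.6% with Wilson and 78.2% with Clopper-Pearson, so only Wald clears 80%. At 47, 48 and 49 of 50 the Wald upper limit exceeds 100% (100.6%, 101.4%, 101.9%).

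**4. What an observed 80% can show.** With 50 independent patients, P(X ≥ 40) is 7.9% at a true 70%, 26.2% at 75%, 58.4% at 80%, 88.0% at 85% and 99.1% at 90%. A rule that the Wilson lower limit must exceed 80% needs 46/50. P(X ≥ 46) is 1.9% at a true 80% and 43.1% at a true 90%.

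**5. Aim 1a.** The study has one arm and states no reference success rate; the 14 earlier patients in section 2.4 are described only by toxicity. An overall change therefore cannot be computed. If it means change between administrations, it repeats 1b, and the Analysis text then contains no estimate of the incidence itself.

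**The case against.** The printed width is correct arithmetic, and at 40/50 Wilson moves each limit by only about 2 points. The Wald shortfall is 1.2 points at the planning value. The 87.9% at a true 90% is a local trough (91.7% at 0.89, 94.3% at 0.91), and Wilson also dips below 95% at some rates (93.2% at 0.81). All this stands. The case for Wilson rests on the one-sided misses and on naming a method in advance, not on the worst coverage figure. An exact interval would also be defensible, at a width of 0.237.

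A reader might infer that 80% is a study-level pass mark. The documents do not support that. Section 9.3 states an estimation objective, success is defined per infusion elsewhere, and nothing is made to depend on reaching 80%. The figure probably comes from the hypothesis in section 1.3. The probabilities in step 4 of the working therefore describe a possible misreading, not a rule in the plan.

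A reader might also infer that the primary aim has no analysis. That goes too far: read grammatically, the GEE sentence covers Aim 1a. What is missing is a computable target for it. GEE with robust errors would also handle pooled infusions properly, but section 9.1 puts the primary endpoint at the first cycle, where pooling does not arise.

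**Conclusion.** The point holds as a mismatch between the planned precision and the primary endpoint. The 69%–91% interval applies directly only if 50 distinct patients each contribute one first-cycle infusion, and sections 9.1, 9.2 and 9.3 do not ensure this. With an assumed 25 to 60 patients, the Wilson width at 80% runs from 0.30 to 0.20. The unnamed interval method is a smaller matter at 80%, but it can change the reading near 90%, as 45/50 shows. The definition of success and the wording of Aim 1a are mainly drafting faults that other sections allow a reader to repair. The coverage and tail figures assume independent patients with a common success rate.

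**What to change.** 1. **Section 9.3, Analysis.** Take Aim 1a out of the GEE sentence. State it as the proportion of patients whose first-cycle end-infusion level is in the target range, with a two-sided 95% Wilson interval. Keep GEE for 1b, 1c and any estimate that pools several infusions per patient. Section 9.3 also uses cycle for a block with an infusion every two weeks, so say explicitly which single infusion counts.
2. **Section 9.3, sample size.** Define success for one infusion. Replace the 69%–91% sentence by: *If 50 patients contribute a first-cycle infusion and 40 are in range, the Wilson 95% CI is 67% to 89%.* Add the widths for other plausible patient numbers.
3. **Sections 9.1, 9.2 and 9.3.** Use one unit. Either fix the number of first-cycle patients or state that it is open and that precision will vary. Say whether infusions needing no adjustment enter the primary analysis.
4. **Sections 1.3 and 9.3.** Either call 80% a planning value and judge the hypothesis only through the interval, or state a decision rule with its error rate. A point estimate of 40/50 or more should not by itself be called support.

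**Cost.** Items 1, 2 and 4 are wording, with a slightly less favourable printed interval and a more modest claim near 80%. The planned width of 0.22 survives only with about 50 first-cycle patients; guaranteeing that number means changing the accrual rule in section 9.2. A rule based on the lower limit would be demanding: 46/50, met 43% of the time at a true 90%.
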